6.1.1.4 Double-blind Discontinuation Period

The Double-blind Treatment Period will be followed by a 2-week Discontinuation Period, during which no study drug will be administered and patients will be monitored for potential physical dependence, as follows:

- Daily patient completion of the Short Opiate Withdrawal Scale (ShOWS-Gossop 1990) (paper worksheet to be filled by each patient at home on nondialysis days and at the dialysis unit on dialysis days at similar time of the day for a given patient) (see worksheet in Appendix 6, Section 14.6)
- Completion of an Objective Opiate Withdrawal Scale (OOWS) worksheet (Handelsman 1987) by a trained observer at each dialysis visit (ie, 3 times a week) (see worksheet in Appendix 7, Section 14.7) (training of observer will be recorded)
- Recording of adverse events, medication used, body temperature, and vital signs at each dialysis visit.

Measurements will be taken starting at the end of the Treatment Period (Day 85) and then at each dialysis visit for up to 2 weeks following study drug discontinuation until Day 98 (Table 2).

During this Discontinuation Period, at each dialysis visit, patients will be asked to continue to report their daily Worst Itching Intensity NRS score over the previous 24 hours. In order to minimize bias, the OOWS and ShOWS will be introduced to the patients as health-assessment scales.

On the day of a dialysis visit, the OOWS and the ShOWS will be completed during the first hour (+1-hour window allowed) of dialysis so that dialysis-associated patient fatigue should minimally interfere with the completion of the scales. Double-blind study drug treatment assignment will remain blinded throughout the course of the Discontinuation Period. For patients who withdraw from the Double-blind Treatment Period early, every attempt will be made to conduct the 2-week Discontinuation Period.

A Structured Safety Evaluation will be performed weekly (preferably on Wednesday/Thursday) during the Discontinuation Period. The Structured Safety Evaluation is performed by study staff using a list of specific signs/symptoms (eg, mental status change, falls, gait disturbance).

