Record dose of ESA and IV iron	X		Record on an ongoing basis						X		
Record number of missed dialysis visits and reason(s)			Record on an ongoing basis								
IV administration of study drug			Record on an ongoing basis								
Inflammatory biomarker samples ^o			X						X		
Adverse event monitoring	X	X	Record on an ongoing basis						X	X	
Concomitant medications (including antipruritic medications) ^p			X	Record on an ongoing basis						X	X
Structured Safety Evaluation ^f		X		X			X			X	

DP = Discontinuation Period; ESA = erythropoiesis-stimulating agent; F = Friday; IV = intravenous; M = Monday; NRS = numerical rating scale; OOWS = Objective Opiate Withdrawal Scale; PRO = patient-reported outcome; Sa = Saturday; ShOWS = Short Opiate Withdrawal Scale; Th = Thursday; Tu = Tuesday; W = Wednesday

-
- a. Each visit during the Double-blind Treatment Period will coincide with the patient's normal dialysis treatments.
 - b. The End-of-Treatment Visit in the Double-blind Phase will be the first dialysis visit following the last dose of study drug (ie, first dialysis on Week 13 [Day 85]), which also corresponds to Day 1 of the Discontinuation Period (DP Day 1).
 - c. Medical history will be updated on Day 1 with any changes since the Screening Visit, and inclusion/exclusion criteria will be confirmed prior to randomization. Antipruritic medication will be updated at each dialysis visit during the Run-in Period.
 - d. Electrocardiogram must be performed prior to the start of dialysis at screening, Day 85 (End of Treatment), or at Early Termination visit.
 - e. Pre-dialysis vital signs, including body temperature, heart rate, and blood pressure, will be recorded on Days 1, 15, 29, 43, 57, 71 and 85 (End of Treatment), or at Early Termination visit only when the patient is in a sitting or semi-recumbent position. Heart rate will be measured at each dialysis; if heart rate is clinically significant and outside the prespecified visits per Schedule of Events, the heart rate will be recorded on the relevant CRF page.
 - f. Pre-dialysis vital signs, including body temperature, heart rate, and blood pressure, will be recorded at each dialysis visit during the Discontinuation Period. Heart rate will be measured at each dialysis.
 - g. Blood samples for clinical laboratory evaluation will be taken at screening, and on Days 1 and 85 (End of Treatment), or at Early Termination visit only.

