8.9.4 Discontinuation Period Additional Assessments

Baseline ShOWS and OOWS will be the scores collected on the dialysis day on Day 85 (Double-blind EOT/Early Termination) (Table 2). Only patients who have a baseline ShOWS and OOWS will be included in the analysis.

Summary statistics for the daily ShOWs and the OOWS collected at each dialysis visit, including number of non-missing observations, mean, standard deviation, median, minimum, and maximum median of ShOWS and OOWS will be tabulated by treatment group. Figures for the overall mean scores over time will also be presented.

The ShOWS scores on discontinuation days 1, 2, 3, and >3 will be analyzed to compare the treatment groups at each visit, using an Analysis of Covariance (ANCOVA) model, with treatment group and baseline value as a covariate. The OOWS scores will be analyzed using a similar ANCOVA model at each day of collection. In addition, between-treatment group comparisons over the overall 2-Week Discontinuation Period will be performed using an MMRM with treatment group, discontinuation day, and treatment group-by-day interaction as fixed effects, baseline value as the covariate, and patient as a random effect. An unstructured covariance matrix will be used to model the covariance of within-patient scores. These analyses will be performed based on all postbaseline scores using only the observed cases without imputation of missing values.

Exploratory analyses may be performed, depending on sample size, for the subgroup of patients who also stop taking concomitant opioid medications during the 2-week Discontinuation Period.

Adverse events (AEs) and vital signs potentially related to withdrawal that occur during the 2-week Discontinuation Period will be identified based on a blinded review of the data, and will be summarized by randomized treatment group, and compared to the 2-week period prior to discontinuation.

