9.5 Vital Signs, and ECG

9.5.1 Vital Signs

Summary tables for vital signs will include descriptive statistics (number of subjects, mean, standard deviation, median, minimum, and maximum) for baseline and each post-baseline assessment. Descriptive statistics will be calculated on both the actual values and the change from baseline. Baseline is defined as the last measurement taken on or prior to the first day of dosing. Note that the Day 1 assessment can be included in the evaluation of baseline given that the assessment is performed prior to dosing.

All double-blind vital sign summaries will include the subjects in the Double-blind Safety Population or Double-blind Discontinuation Safety Population who have at least 1 post-baseline assessment (for criteria based on post-baseline assessments) and with both a baseline and at least 1 post-baseline assessment (for criteria evaluating changes from baseline).

Clinically notable vital signs will be identified based on the criteria below. For each vital sign parameter, the number and percentage of subjects with at least 1 notable value will be tabulated by week and overall for the Double-blind Treatment Period and Discontinuation Period separately.

Vital Sign Parameter	Value
Systolic blood pressure	≥180 mm Hg
	≤90 mm Hg
Diastolic blood pressure	≥100 mm Hg
	≤60 mm Hg
Heart rate	>130 bpm
	<55 bpm

bpm = beats per minute

All vital signs will be listed in by-subject listings, including visit and collection date/time, and will be sorted by subject identifier and date/time of assessment.

9.5.2 12-Lead ECGs

Standard 12-lead ECG readings with the subject in a supine position will be performed. Electrocardiogram results include an overall interpretation of “normal,” “abnormal but not clinically significant,” or “abnormal and clinically significant.” These results will be tabulated by treatment group and overall at each time point. Electrocardiogram values will also be listed by subject.

Clinically significant abnormalities at screening will be recorded as medical history. Clinically significant abnormalities or worsening of ECG findings observed after the first dose of study drug should be reported as adverse events.

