12. CHANGES TO THE ANALYSES PLANNED IN THE PROTOCOL

- The protocol defines clinically notable vital signs based on values observed at the visit and on change from baseline. The definition was updated to remove the criteria based on change from baseline since it was deemed not necessary.
- The protocol states that Akaike information criterion will be used to select the appropriate covariance matrix structure for the MMRM analysis. The SAP uses an unstructured covariance matrix structure as the first choice. Should the model fail to converge, a compound symmetric covariance matrix will be used instead.
- Throughout the protocol, MMRM analyses state that random subject effects will be used, but also provide R-side matrix structures, rendering the random effect (GZ matrix) unnecessary. Random effects have therefore been removed throughout.
- The protocol states that the ShOWS scores on Discontinuation Period Days 1, 2, and 3 and days after Day 3 will be compared between treatment groups using an ANCOVA model. Because scores taken on Day 1 of this period will be included in the model as the subject's baseline score, this analysis was revised to compare ShOWS scores on Discontinuation Period Days 2, 3, and 4, 5, 6 and average assessment on days after Day 6. Additionally, the MMRM analysis was dropped, a categorical analysis was added for OOWS, and text clarifying the OOWS collection times was added.
- The protocol states that adverse events and vital signs potentially related to withdrawal that occur during the 2-week Discontinuation Period will be compared to the adverse events and vital signs reported during the 2-week period preceding the Discontinuation Period. Per the SAP, no comparison to the 2-week period prior to the Discontinuation Period will be made.
- The rules of mapping the early termination visit and the unscheduled visits into a scheduled visit based on visit windows were clarified in the SAP. The protocol states that if 2 or more evaluations occur in the same visit window, the evaluation closest to the target visit day will be selected for inclusion in the analysis. This was revised to select the non-missing value in the order of scheduled visit, early termination visit, and the unscheduled visits.
- The Double blind Discontinuation and Double blind Discontinuation Safety Populations were added.

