DP = Discontinuation Period; EOT = end of treatment; ESA = erythropoiesis-stimulating agent; F = Friday; IV = intravenous; M = Monday; NRS = numerical rating scale; OOWS = Objective Opiate Withdrawal Scale; PRO = patient-reported outcome; Sa = Saturday; ShOWS = Short Opiate Withdrawal Scale; Th = Thursday; Tu = Tuesday; W = Wednesday

- a. Each visit during the Double-blind Treatment Period will coincide with the patient's normal dialysis treatments.
- b. The End-of-Treatment Visit in the Double-blind Treatment Period corresponds to Day 1 of the Discontinuation Period.
- c. Medical history will be updated on Day 1 with any changes since the Screening Visit, and inclusion/exclusion criteria will be confirmed prior to randomization.
- d. Electrocardiogram must be performed at screening, and Day 85 prior to the start of dialysis.
- e. Vital signs, including body temperature, heart rate, and blood pressure, will be obtained at the specified visits when the patient is in a sitting or semi-recumbent position prior to the start of dialysis. Heart rate will be collected at each dialysis; if clinically significant and outside the prespecified visits per SOE, the heart rate will be recorded on the relevant CRF page.
- f. Pre-dialysis vital signs will be recorded on Days 1, 15, 29, 43, 57, and 85 only.
- g. Vital signs, including body temperature, heart rate, and blood pressure, will be obtained prior to the start of each dialysis at each dialysis visit during the Discontinuation Period.
- h. Blood samples for clinical laboratory evaluation will be taken on Days 1 and 85 only.
- j. Training on Worst Itching Intensity NRS on the first day of the Run-in Period.
- k. Training on Skindex-10 Scale and 5-D Itch Scale may be performed at any time during the week prior to randomization or on Day 1 of the Double-blind Treatment Period.
- l. Patients will be requested to complete their worksheets each day at a similar time (either at home on non-dialysis days around the normal start time of their dialysis or in the dialysis unit). On dialysis days, the worksheets will be completed prior to or during dialysis, but must be completed prior to dosing of the study drug. During Discontinuation Period, worksheets to be completed on dialysis days only.

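### The SAP drops the protocol's pre-discontinuation comparison without a reason and prespecifies no within-patient change from end of treatment for Discontinuation Period vital signs

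*SAP*

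**What the plan says.** Protocol 6.1.1.4 describes two weeks in which "no study drug will be administered and patients will be monitored for potential physical dependence", with body temperature and vital signs taken at each dialysis visit. Protocol 8.9.4 has a blinded review pick out the adverse events and vital signs that may reflect withdrawal. These "will be summarized by randomized treatment group, and compared to the 2-week period prior to discontinuation". This is the protocol's only pre-discontinuation comparison that covers vital signs. A separate before-and-during table in Protocol 8.8.2 covers adverse events only.

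SAP 12 removes the comparison: "Per the SAP, no comparison to the 2-week period prior to the Discontinuation Period will be made". Some other entries in that list explain themselves; this one does not.

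For vital signs in general, SAP 9.5.1 states: "Baseline is defined as the last measurement taken on or prior to the first day of dosing". The same section applies to the Discontinuation Period: "All double-blind vital sign summaries will include the subjects in the Double-blind Safety Population or Double-blind Discontinuation Safety Population". It also provides that "Descriptive statistics will be calculated on both the actual values and the change from baseline". SAP 3 gives the opiate withdrawal scales a Day 85 baseline and makes no such provision for vital signs.

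On timing, footnote f of SAP Table 4 says: "Pre-dialysis vital signs will be recorded on Days 1, 15, 29, 43, 57, and 85 only". Footnote e of protocol Table 2 lists the same days plus Day 71.

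**The concern.** A dependence assessment asks what happens to a patient when the drug is stopped. The natural quantity is the change from the last on-drug reading to the readings that follow. The SAP uses that logic for ShOWS and OOWS but not for vital signs, whose only planned change score starts before the first dose.

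At a Discontinuation Period visit, that change score contains whatever the drug did over 12 weeks and has not yet worn off, plus anything caused by stopping. A reader shown only this figure cannot tell a lingering drug effect from a withdrawal effect. The number of patients with a marked shift on stopping would not be reported at all.

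**Working it through.** The plan states no figure to reproduce. The check is day arithmetic, a simple decomposition with assumed values, and a look at what the planned tables can and cannot give.

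**1. Age of the reference.** Discontinuation Period Day k is study Day 84 + k, because Day 1 of that period is Day 85. SAP 10.5 gives the dialysis days as 1, 3, 5, 8, 10 and 12, that is, study Days 85, 87, 89, 92, 94 and 96. For a completer:

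- From Day 1, the visits after Day 85 are 87 − 1 = 86 to 96 − 1 = 95 days away.
- From Day 85, they are 87 − 85 = 2 to 96 − 85 = 11 days away.

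**2. What each change score contains.** Let *m* be drift common to both arms, *d* the drug effect at Day 85, *f* the fraction of *d* still present at the later visit, and *w* the withdrawal effect. The CR845 minus placebo differences are:

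- change from Day 1: (m + f·d + w) − m = f·d + w
- at Day 85, change from Day 1: (m + d) − m = d
- change from Day 85: (f·d + w) − d = w − (1 − f)·d

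Drift cancels in all three. With m = 4 in arbitrary units (assumed, since the documents give no vital-sign means or SDs):

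| Case | d | f | w | Change from Day 1, CR845 / placebo | Difference from Day 1 | Difference at Day 85 | Difference from Day 85 |
|---|---|---|---|---|---|---|---|
| (a) withdrawal only | 0 | 0 | 5 | 9 / 4 | 5 | 0 | 5 |
| (b) drug effect persists, no withdrawal | 5 | 1 | 0 | 9 / 4 | 5 | 5 | 0 |
| (c) drug effect wears off, no withdrawal | −5 | 0 | 0 | 4 / 4 | 0 | −5 | 5 |

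Cases (a) and (b) look identical on change from Day 1 at the later visit. The Day 85 column, or a change from Day 85, tells them apart. Case (c) is the warning the other way: change from Day 85 shows +5 when nothing has happened except ordinary offset of drug effect. Neither score isolates *w* alone, so the two need to be read together.

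**3. What subtracting tabulated means leaves out.** If the same patients contribute, the mean change from Day 85 equals the difference of two tabulated means. Three things are not recoverable from the summary tables.

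- *Spread.* With equal SD *s* at both visits and within-patient correlation ρ, the SD of the change is s·√(2(1 − ρ)). The tables do not give ρ. Over an assumed range of 0.3 to 0.7 this runs from √1.4·s = 1.18s down to √0.6·s = 0.77s.
- *Patient set.* Under SAP 9.1, treatment-period tables use the Double-blind Safety Population and discontinuation tables use the two discontinuation populations. A Day 85 mean from the former need not describe the patients in the latter.
- *Counts by size of change.* Notable values in SAP 9.5.1 now rest on absolute limits alone. As an illustration, a heart rate moving from 60 to 100 bpm crosses neither limit (above 130, below 55). The protocol's change criterion had to be met together with the value limit, so removing it flags more readings, not fewer. But no SAP output counts patients by how far they moved.

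**4. Readings before stopping.** In Days 71 to 84 the protocol schedules one vital-sign reading (Day 71) and the SAP schedule shows none. Day 85 is in both. SAP 8.2.4.3 notes that the last dose of a week is not cleared until the next week's first dialysis, so the Day 85 pre-dialysis value is still an on-drug value.

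**The case against.** The strongest reply has five parts, and much of it stands.

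- *The baseline was not created by the SAP.* Protocol 8.8.4 has the same pre-first-dose definition. A reader might infer that dropping the comparison changed the vital-sign baseline. It did not; it left that baseline as the only reference.
- *The information is not lost.* A reader might infer that withdrawal can no longer be separated from drug effect and drift. That is too strong. Drift is shared with the randomised placebo arm. Actual values are tabulated by arm and visit including Day 85, and every value is listed by patient. What is missing is a prespecified within-patient summary.
- *Change from Day 1 may be the better measure of rebound.* Protocol 4.2.4 describes plasma levels that stay fairly constant until dialysis clears the drug, with little or no accumulation. If the effect goes with the drug (f = 0), the difference from Day 1 equals *w*, and the difference from Day 85 equals w − d, which would present offset as withdrawal. This stands, and it is why change from Day 1 must be kept. The documents do not establish that vital-sign effects follow plasma levels that closely.
- *The dropped comparison was weak for vital signs.* It would have set one scheduled reading against five (Days 87, 89, 92, 94 and 96), so counts of flagged values would have been unequal by design. Day 71 is also two weeks older than Day 85 as a reference. Both points stand.
- *The footnote is editorial.* SAP primacy in Section 1 concerns analyses, and collection follows the protocol. Agreed, but the two schedules should still match.

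**Conclusion.** The point holds as a cheap improvement. No prespecified vital-sign output describes the within-patient change on stopping drug, although such outputs exist for ShOWS and OOWS and the data are already collected. The only comparison in that direction was removed without explanation.

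The size cannot be put in clinical units, because the documents give no vital-sign means, SDs or correlations. What can be stated is the age of the reference (86 to 95 days instead of 2 to 11, for completers) and the ambiguity shown by cases (a) and (b). Those cases assume additive effects and drift common to both arms.

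Two further inferences are not supported. A reader might conclude that the dependence assessment as a whole could come out falsely negative. The documents do not bear this out: ShOWS and OOWS are analysed from Day 85 with ANCOVA, the SAP adds a blinded review of withdrawal-type adverse events, and vital signs are one component beside these. A reader might also conclude that change from Day 1 must be less precise by some known amount. That would depend on correlations the documents do not give, and no inference on vital signs is planned.

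**What to change.** In SAP 9.5.1, for both the Double-blind Discontinuation Safety Population and the Double-blind Discontinuation Population, add by arm and visit the change from the Day 85 (or Early Termination) pre-dialysis value, restricted to subjects with both readings. Show it beside change from the pre-first-dose baseline. Add a note that change from Day 85 includes ordinary offset of drug effect and that the two columns are to be read together. Protocol 6.3.1 allows a late Early Termination Visit, so identify reference readings not taken at the first dialysis after the last dose.

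In SAP 12, give the reason for dropping the Protocol 8.9.4 comparison. In SAP Table 4, correct footnote f to include Day 71, matching footnote e of protocol Table 2.

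The cost is SAP wording and one more table per vital-sign parameter. No new data are needed. The downside is that a change from Day 85 read alone could be mistaken for withdrawal, hence the paired display.

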13. RANDOM SEEDS FOR MULTIPLE IMPUTATION

For MIs and other instances where random seeds are required, the values used (in order) are:

8392857
2985729
1843255
9086284
5547484
8017456
9597295
2252256
4821871
9852467
5126715
3232132
9841654
3645284
1587345

Note that not all seeds may be required in programming the MIs. If additional seeds are needed, they will be chosen by adding 1 to each of the values above, again using them in order.

14. SAMPLE SAS CODE

Below is the SAS code used to create the dataset to be used in the primary analysis. Weekly NRS scores will be subset on the ITT Population and the dataset will be transposed to create one observation per subject with separate variables for baseline (v1) through week 12 (v13) values. These values as well as a numeric variable for the planned treatment group (trt01pn) and numeric flags for anti-itch medication use at baseline (antiIn) and specific medical conditions (specmedn) will be used during the imputation procedures.

The first stage of imputation will create monotone missing data using MCMC and the following code:

```
proc mi data=INDATA seed=8392857 nimpute=20 MAXIMUM=10 MINIMUM=0
out=OUTDATA1 minmaxiter=1000000 ;
mcmc chain=multiple initial = EM(CONVERGE=0.001 maxiter=100000) NBITER=500
NITER=100 impute = monotone displayinit ;
var antiIn specmedn v1 v2 v3 v4 v5 v6 v7 v8 v9 v10 v11 v12 v13;
by trt01pn;
run;
```

Using the output data, imputed data following the last non-missing will be reset to missing so that only intermittent values are imputed in this first pass.

The second stage will use this output, then fill in the monotone missing values with the following MI code:

```
proc mi data=OUTDATA1 seed=2985729 nimpute=1 MAXIMUM=10 MINIMUM=0
out=OUTDATA2 minmaxiter=1000000 ;
monotone reg;
var antiIn specmedn v1 v2 v3 v4 v5 v6 v7 v8 v9 v10 v11 v12 v13;
by trt01pn;
run;
```

